08.03.2021

**The Effect of Music Integrated Phonological Awareness
Program on Phonological Awareness Skills of Preschool (5-6
Years) Cochlear Implant Users**

Study Protocol and Statistical Analysis

A. Official Title of the Study:

The Effect of Music Integrated Phonological Awareness Program on Phonological Awareness Skills of Preschool (5-6 Years) Cochlear Implant Users

B. Rationale and Purpose of the Study:

Reason for this study: There is a study in the literature that provides music-integrated phonological awareness training with normal-hearing children and investigates the effect of phonological awareness, but there is no study that observed the effect of phonological awareness after musicintegrated phonological awareness training in preschool children using cochlear implants.

The aim of this study; The aim of this study is to apply a music-integrated phonological awareness education program to 5-6 year old children using cochlear implants and to examine the effect of education on phonological awareness skills.

C. Main Study Form:

C.1.1. General Information:

Phonological awareness is a comprehensive skill in recognizing and using the units of oral language (Soleymani, Mahmoodabadi, & Nouri, 2016). Phonological awareness skill requires the analysis of speech sounds, either alone or in words, expressions, sentences, as independent phonemes (Saad, 2013).

Phonological awareness skills begin in the preschool period and continue to develop during the school period (Carroll, Snowling, Stevenson, & Hulme, 2003). Therefore, it is an important component of education that should be addressed in order to prevent reading difficulties that may occur in children during academic education (Phelps, 2003).

To perceive both music and language, it is necessary to be able to distinguish sounds. Sounds can be characterized by certain spectral feature. These spectral features are found in both musical and linguistic sounds (Pesnot Lerousseau, Hidalgo, & Schön, 2020).

Being aware of the fact that the units in the music can be broken down into smaller parts is an important skill to be acquired before manipulating the verbal units (Davis, 2019).

It is known that music education improves language skills without focusing on existing deficiencies (Patscheke, Degé, & Schwarzer, 2016). There are extensive studies in the literature showing that teaching music facilitates the development of language skills in general and reading skills in particular (Herrera, Quiles, Defior, Fernández Smith, & Costa-Giomi, 2011).

Studies have suggested that some auditory analysis skills used in language processing, such as combining and separating phonemes, are similar to the skills required for music perception, such as rhythmic, melodic and harmonic discrimination (Anvari, Trainor, Woodside, & Levy, 2002).

Children with congenital hearing loss rely on auditory input delivered through a hearing aid or cochlear implant to hear speech structures. A hearing aid (HA) amplifies sounds to an audible level. This increases a child's access to time-varying spectral information of speech recognition structures and phoneme changes to support the acquisition of phonological skills. As hearing loss increases, the ability to receive information from an audible signal decreases (Ching, Dillon, Katsch, & Byrne, 2001).

Recent studies in children with severe or profound hearing loss have focused on evaluating the effectiveness of cochlear implantation. There is general agreement that children using cochlear implants perform within the normal range for tasks involving syllable counting or tracking, but exhibit deficits for tasks that require phoneme-level perception and manipulation (Ching, Cupples, 2015).

Individuals with hearing loss have limitations in understanding the phonological knowledge of speech. For this reason, the reading and writing development of hearing impaired individuals is not at the desired level (Chelsea, 2014).

Many studies have been done; shows the relationship between musical skills, phonological awareness and literacy abilities. (Bhide et al., 2013; Christiner & Reiterer, 2018; Herrera et al., 2011; Krau et al., 2014; Moritz et al., 2013).

C.1.2. Materials and Methods C.1.2.1.

facts

23 children with cochlear implants and 23 with normal hearing will be included in the study.

Inclusion Criteria:

☐ Bilateral severe sensorineural hearing loss and those who use unilateral or bilateral cochlear implants

☐ To be between 5-6 years old

☐ To have receptive and expressive language at the level of their peers from the language test to be made

☐ Regular users of cochlear implants

Exclusion Criteria:

☐ Not meeting any of the inclusion criteria for the working group,

☐ Having an additional disability

☐ Those who use drugs that may affect the auditory system

C.1.2.2. Methods to be Used in the Study

a. Laboratory and clinical evaluation methods to be used in the study

All participants will be given language assessment, spectral-temporary modulated ripple test (SMRT) and phonological awareness and auditory evoked late potential tests.

Participants' phonological awareness skills will be evaluated with a standardized phonological awareness scale consisting of 78 questions. The language test will be used for language assessment. Auditory evoked evoked late potentials will be recorded in a quiet room using the Neuron-Spectrum5 (4/EPM) (Neurosoft, Ivanoco, Russia) device.

b. Statistical methods envisaged to be used in the study

Statistical analysis of the results obtained will be made using IBM® SPSS® Statistics v24 (IBM, Armonk, New York, USA). After the normal distribution analysis of the results obtained, correlation analysis, inter-experimental, pairwise and triple statistical comparisons will be performed in accordance with the distribution of the data.

It was planned to use Mann Whitney U test for intergroup comparisons and Wilcoxon test for intragroup comparisons. The values obtained in the study will be presented as mean±standard deviation.

D. Protocol:

D.1. Work Start Date: March 2021

D.2. Duration of Study: At least 3 months

D.3. Locations of the Study: Istanbul University-Cerrahpaşa Medical Faculty Audiology and Speech Disorders Clinic

D.4. Study Coordinators:

Study Advisor: [name]

Study Coordinator: [name]

E. Project Achievements, Ethical and Legal Requirements:

E.1. Learning Outcomes: The effect of the Music Integration Phonemic Awareness program on the phonological awareness skills of pre-school (5-6 years old) cochlear implant users will be examined.

E.2. Informing the Ethics Committee:

E.3. Records Retention and Quality Assurance Measures:

All data obtained will be stored in accordance with the privacy policy. The data to be obtained will not be made public. In the data to be used in the study, the names of the individuals will be kept confidential.

The standard follow-up and treatment of the patients will not be affected by this study.

F. Resources

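### The plan describes no untrained implanted comparison: if all 23 implanted children are trained, its tests cannot by themselves attribute change to the programme, and no limit is set on that conclusion

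*Combined protocol and SAP*

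**What the plan says.** Section B says the programme is given to implant users aged 5 to 6, and that the purpose is "to examine the effect of education on phonological awareness skills". E.1 repeats the target as "The effect of the Music Integration Phonemic Awareness program on the phonological awareness skills" of these children, and the official title also speaks of the programme's effect.

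C.1.2.1 gives the groups in one sentence: "23 children with cochlear implants and 23 with normal hearing will be included in the study". The document mentions no allocation, waiting list, delayed start, repeated baseline or untrained implanted children. It gives no assessment times and does not say whether the normal-hearing children are trained or retested.

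The named tests in C.1.2.2b are these: "It was planned to use Mann Whitney U test for intergroup comparisons and Wilcoxon test for intragroup comparisons". The sentence before it also lists inter-experimental and triple comparisons without saying what is compared. One exclusion criterion, "Not meeting any of the inclusion criteria for the working group", uses a group name that is defined nowhere.

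Four other statements bear on the point:

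- C.1.1 on development: "Phonological awareness skills begin in the preschool period and continue to develop during the school period".
- C.1.1 on implanted children, who "perform within the normal range for tasks involving syllable counting or tracking, but exhibit deficits for tasks that require phoneme-level perception and manipulation".
- The inclusion criterion on language: "To have receptive and expressive language at the level of their peers from the language test to be made".
- E.3, which says that usual care carries on unchanged.

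No section limits what may be concluded from a change in scores.

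**The concern.** The question is causal: what does the programme do for implanted children? Answering it needs some estimate of how these children would have scored over the same period without the programme. The plan describes no implanted children who could supply one.

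The outcome is also one that the protocol itself expects to improve with age. The study runs for at least 3 months (D.2), the only phonological awareness measure named is a single 78-question scale (C.1.2.2a), and usual care continues.

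On the natural reading, a significant before-after result could therefore arise with a programme that does nothing. A comparison with normal-hearing children could mislead in either direction: unequal natural growth can mimic an effect, or hide a real one. No later analysis can supply a comparison that was never collected, so the limit on the conclusion belongs in the plan.

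**Working it through.** **No figure to reproduce.** The 23 + 23 comes without an effect size, power, SD or dropout rate. The point is one of design, so the first step is what each test estimates.

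**What each test estimates.** Let τ be the programme effect in implanted children. Let g_CI and g_NH be the gains that implanted and normal-hearing children would make anyway, from development, practice and usual care.

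| Analysis | Quantity tested against zero | Equals τ only if |
|---|---|---|
| Wilcoxon, before v after, implanted | τ + g_CI | g_CI = 0 |
| Mann-Whitney on change, normal-hearing untrained and retested | τ + g_CI − g_NH | g_CI = g_NH |
| Mann-Whitney on change, normal-hearing also trained (effect τ_NH) | τ − τ_NH + g_CI − g_NH | τ_NH = 0 and g_CI = g_NH |
| Mann-Whitney on scores after the programme | baseline difference + τ + g_CI − g_NH | baselines and natural gains are equal |

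C.1.1 makes g_CI = 0 implausible. The document does not establish g_CI = g_NH. The language criterion and the statement on syllable tasks bring the groups closer, but the same sentence reports phoneme-level deficits. All three are statements about level, and equal level would not show equal growth.

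**Illustration of size.** The document gives no growth rate and no correlation between repeat scores, so every gain below is an assumption. Change scores are normal, tests are two-sided at 5%, and each cell was simulated; repeat runs agreed to within about one percentage point.

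Inert programme (τ = 0), Wilcoxon signed-rank, n = 23:

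| Background gain (SD of change) | 0 | 0.1 | 0.2 | 0.3 | 0.5 | 0.8 |
|---|---|---|---|---|---|---|
| Trials significant | 5% | 7% | 15% | 27% | 61% | 95% |

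To convert to raw-score SD, multiply by √(2(1 − r)), where r is the assumed before-after correlation: 0.775 at r = 0.7 and 0.632 at r = 0.8. A gain of 0.5 SD of change is then 0.39 or 0.32 raw SD, and 0.1 SD of change is 0.08 or 0.06 raw SD.

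Inert programme, Mann-Whitney on change, 23 v 23:

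| Difference in natural gain (SD of change) | 0 | 0.2 | 0.3 | 0.5 |
|---|---|---|---|---|
| Trials significant | 5% | 9% | 16% | 36% |

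At zero difference this test keeps its nominal 5%, so it is valid when its assumption holds.

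**Masking.** The same table covers a real effect of τ = 0.5. With equal natural gain the shift is 0.5 and the effect is detected about 36% of the time. If normal-hearing children gain 0.3 more, the shift is 0.5 − 0.3 = 0.2, giving about 9%. If they gain 0.5 more, the shift is 0, giving about 5%.

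**The case against.** The best defence is that the normal-hearing children are the concurrent control for maturation and practice. Part of this stands. If they are untrained and retested, and change is compared, shared growth and practice cancel. But the document states none of these conditions, and the remaining one, equal natural gain, is unsupported. A reader might go further and infer that the normal-hearing group is useless as a control. That is also too strong, because under equal gain the test is sound.

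A second defence is that the undefined terms (inter-experimental, triple, working group) may point to a split of the implanted children. This cannot be excluded. A reader might infer that all 23 are certainly trained, or conversely that the document is silent on who is trained. Neither is right: B names implanted children as recipients, but does not say that all of them are. No split is described either, so the attribution problem is conditional on the natural reading.

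A third defence is that the plan only undertakes to examine an effect and sets no rule for claiming one. That is fair, and the document does not commit the sponsor to a causal claim. Still, the aim is worded causally and nothing restrains the conclusion.

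Finally, the scale is called standardized (C.1.2.2a). Age norms could show whether gains exceed those expected with age. The document does not say that norms exist, and norms would not remove practice effects.

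**Conclusion.** The concern holds in conditional form. As described, and if all 23 implanted children are trained and tested before and after, neither named test by itself separates a programme effect from background gain, and the plan sets no limit on the conclusion.

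The size depends on gains that the document does not give. With an inert programme, the chance of a significant Wilcoxon result runs from barely above nominal (7% at 0.1 SD of change) to near certainty (95% at 0.8). For Mann-Whitney on change it runs from 5% with equal natural gain to 36% at a difference of 0.5. These figures illustrate the logic and do not predict this trial's error rate.

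A reader might infer that the study is invalid or must be redesigned. The document does not support that: a before-after description in implanted children remains a legitimate result if it is labelled as one. The wording should be fixed in any case, and must be if the natural reading is confirmed. Confidence is medium because of the undefined terms.

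**What to change.** 1. In C.1.2.1, state whether all 23 implanted children are trained, whether the normal-hearing children are trained, and when each group is tested. Define the three unclear terms.

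2. Unless this shows a comparison that separates the programme from background gain (such as concurrent untrained implanted children), add to C.1.2.2b:

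> *Pre-post results in the implanted group will be reported as change during the programme and not attributed to it. Any difference in change from untrained, retested normal-hearing children will be read as a programme effect only under the stated and untested assumption of equal natural gain.*

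3. Word the aim in B and the outcome in E.1 to match. Either align the title or note that it is descriptive.

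4. If the implanted children are split, name trained v untrained implanted children as the deciding comparison and state how they were allocated.

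5. If the scale has age norms, report scores against them as partial support.

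The cost is a short amendment and a weaker conclusion, with no extra children, visits or tests.

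A delayed start within the 23, or two baseline tests before the programme, would give a cleaner comparison. Both are optional trade-offs and not part of the required fix. They lengthen the study and have low power. For a 12 v 11 split, the difference detectable with 80% power (two-sided 5%, normal approximation) is (1.960 + 0.842) × √(1/12 + 1/11) = 1.17 SD of the measure compared.
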